I agree to conduct this study according to this protocol and to comply with its requirements, subject to ethical and safety considerations and guidelines, and to conduct the study in accordance with International Conference on Harmonisation guidelines on Good Clinical Practice and with the applicable regulatory requirements.

I understand that failure to comply with the requirements of the protocol may lead to the termination of my participation as an investigator for this study.

I understand that the sponsor may decide to suspend or prematurely terminate the study at any time for whatever reason; such a decision will be communicated to me in writing. Conversely, should I decide to withdraw from execution of the study I will communicate my intention immediately in writing to the sponsor.

Investigator Name and Address:

(please hand print or type)

Signature:

Date:

SUMMARY OF CHANGES FROM PREVIOUS VERSION

| 
A description of the changes are described in the table below; however, minor changes to wording, style, and formatting that do not affect the study design and operations are not described.
 | | |
|--|--|--------|
| 
Summary of Change(s) Since Last Version of Approved Protocol
 | | |
| Amendment Number | Amendment Date | Global |
| 1 | 21 Mar 2017 | |
| Description of Change and Rationale | Section(s) Affected by Change | |
| 
Non-Hispanic, Caucasian subjects will be matched to subjects of Japanese descent based on sex (1:1 male: female), age (± 5 years), weight ($\pm 10\%$), and body mass index ($\pm 15\%$)
 
Reason for Change:
 
The use of the BMI matching criteria, as opposed to weight, is a more common approach in ethnobridging studies and is accepted by the PMDA. Thus weight was removed.
 
Increase in age range to facilitate identification of matches.
 | 
Synopsis: Number of Subjects Synopsis: Methodology Section 3.1 Study Design and Flowchart
 | |
| 
2.2.3 Exploratory Objective
 
To evaluate the PK similarity of rhPTH[1-84] administered as a single SC dose at 25μg and 50μg between healthy adult volunteer subjects of Japanese descent and matched, non-Hispanic, healthy, adult Caucasian subjects using dose-normalized PK data.
 
Reason for Change:
 
Addition of exploratory objective
 | 
Synopsis: Objectives, Section 2.2.3 Exploratory Objectives
 | |

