3. STUDY DESIGN

3.1 Study Design and Flow Chart

This is a Phase 1, open-label, randomized, cross-over, single-center study to evaluate the PK and PD profiles and safety and tolerability of rhPTH(1-84) administered in healthy adult volunteer subjects of Japanese descent and matched non-Hispanic, Caucasian healthy adult volunteer subjects. The non-Hispanic, Caucasian volunteers will receive a single dose of 100 μ g rhPTH(1-84). The Japanese subjects will receive 3 single doses of rhPTH(1-84). On Day 1 the subjects of Japanese descent will receive a single SC injection of 100 μ g. On Days 4 and 7 the subjects of Japanese descent will be randomized to receive a single SC injection of either 25 μ g or 50 μ g, such that all of these subjects are exposed to the 3 dose strengths over a 7-day period to further characterize the PK profile in that group. A total of 24 subjects will be enrolled: 12 non-Hispanic, Caucasian subjects and 12 subjects of Japanese descent (1:1 male: female). Non-Hispanic, Caucasian subjects will be matched to Japanese subjects based on sex, age (\pm 7 years), and body mass index (\pm 15%).

All subjects will receive a single dose of 100 μ g rhPTH(1-84) administered by SC injection in the mid-thigh with the Haselmeier injector pen on Day 1. In addition, the subjects of Japanese descent will also receive single dose injections of 25 μ g and 50 μ g rhPTH(1-84) administered by SC injection in the mid-thigh to characterize the PK profile over a range of doses. There will be a minimum of 72 hours (maximum 73 hours washout from single dose to single dose for the volunteers of Japanese descent. The study duration will comprise of a 28-day screening period, 1 treatment period for the non-Hispanic, Caucasian group (Days 1 and 2); 1 treatment period for the volunteers of Japanese descent (Days 1-8), and a follow-up visit (30 \pm 2 days) after the last dose of investigation drug is administered for each subject. The total number of nights subjects will be expected to stay at the clinical research center (CRC) is 2 for the non-Hispanic, Caucasian group and 8 for the volunteers of Japanese descent. The maximal total duration of study participation for a non-Hispanic, Caucasian subject is 62 days and 68 days for the volunteers of Japanese descent, if the maximum screening, treatment and follow-up visit durations are used.

Screening will occur within 28 days of the first dose. Subjects will be admitted to the CRC on Day -1.

Treatment Period:

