- On Day 1, all study subjects will receive rhPTH(1-84) as a single 100 μ g SC injection in the mid-thigh.
- On Day 4, and Day 7, all subjects of Japanese descent will receive rhPTH(1-84) as a single SC injection in the mid-thigh of either 25 μ g or 50 μ g depending upon randomization assignment. Administration of rhPTH(1-84) in subjects of Japanese descent in the mid-thigh should be randomized locally so that an equal number of subjects receive the first dose in the right thigh and an equal number in the left thigh. Subsequent doses should be administered in the opposing thigh to the last dose.

Assessments

- Serial blood samples for PK analysis will be collected on Day 1 (and Day 4 and Day 7 for the subjects of Japanese descent) for the determination of parathyroid hormone (PTH) concentrations (original and baseline-adjusted) at pre-dose and up to 24 hours post dose. These blood samples will be collected according to the Schedule of Assessments.
- Serial blood samples for PD analysis will be collected on Day 1 (and Day 4 and Day 7 for the subjects of Japanese descent) at pre-dose and up to 24 hours post dose for the determination of serum calcium, phosphate, and albumin concentrations.
- Safety and tolerability will be determined through assessment of treatment-emergent adverse events (TEAEs) from Day 1 time of dose up to the follow-up visit and vital signs, electrocardiogram (ECG) findings, and clinical laboratory evaluations on Day 1 pre-dose and up to 24 hours post dose for the non-Hispanic, Caucasian subjects and Day 1 pre-dose and up to 24 hours post last dose (Day 8) for the subjects of Japanese descent.

[figure not shown]
- Additional blood samples for safety purposes will be collected for assessment of anti-PTH antibodies.

Follow-up

- A post treatment follow-up visit will be completed 30 (± 2) days after the last dose of investigational product for each subject.

Figure 1 Study Design Flow Chart

This is an open-label study to evaluate the PKs, PDs, safety, and tolerability of single doses of rhPTH(1-84) in healthy adult subjects of Japanese descent and matched, non-Hispanic, healthy, adult Non-Hispanic, Caucasian subjects. Group A and Group B need not be dosed at the same time.

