3.2 Rationale for Dose Selection and Study Design Elements

The primary objective of this study is to compare the PK profile of plasma rhPTH(1-84) between subjects of Japanese descent and non-Hispanic, Caucasian volunteers. Although endogenous PTH levels are different between healthy subjects and patients with hypoparathyroidism, historically, evaluations of different formulations, injection devices and dose proportionality, with PK as the primary objective, have been conducted in healthy subjects due to the distinct PK profile of plasma rhPTH(1-84) following subcutaneous administration compared to endogenous PTH. The PK profile of rhPTH(1-84) following subcutaneous administration had been shown to be similar between healthy subjects and patients with hypoparathyroidism in previous studies. Therefore, this study is to be conducted in healthy subjects. Due to the presence of endogenous PTH in healthy subjects and that the current PTH assay measures the total PTH concentration (combination of both endogenous PTH and rhPTH [the assay cannot distinguish between endogenous PTH and administered rhPTH(1-84)]), the PK analysis will be performed based on both the original and baseline-adjusted PTH concentrations. Due to the potential differences in body weight between enrolled subjects of Japanese descent and non-Hispanic, Caucasian subjects, in addition to the non-body weight adjusted PK parameters we will also use body weight-adjusted PK parameters for comparison.

rhPTH(1-84) (Natpara), is currently approved in the US at doses of 25, 50, 75, and 100 μ g administered once daily. rhPTH(1-84) has demonstrated dose-proportional PKs over this dose range in studies performed in the western countries. No significant differences in either the PKs or PDs of rhPTH(1-84) are anticipated between Japanese and non-Japanese; therefore, the 100 μ g dose, the highest marketed dose, will be used in this study for direct comparative purposes. Further doses of 25 μ g and 50 μ g will be used in the subjects of Japanese descent to examine the dose proportionality of PKs in Japanese subjects

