In order to compare the PKs of rhPTH(1-84) between subjects of Japanese descent and matched non-Hispanic, Caucasian subjects, the differences of log-transformed PK parameters from the rhPTH 100ug dose will be examined between groups using an analysis of variance model. The geometric mean ratio and its 90% confidence interval (CI) will be provided from the model. Baseline-adjusted PK parameters will be the primary PK endpoints, and other PK parameters will be the secondary PK endpoints. In addition, the difference of log-transformed dose-normalized baseline-adjusted AUC_{last} and C_{max} will be examined between the Japanese cohort estimated at the 50ug dose and the Non-Japanese cohort estimated at 100ug dose, as well as between the Japanese cohort estimated at the 25ug dose and the Non-Japanese cohort estimated at 100ug dose using an analysis of variance model. The geometric mean ratio and its 90% CI will be provided from the model.

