12.3.4.2 Inferential Analysis of PK Parameters

Comparison of PK between Ethnic Groups

In order to compare the PK of rhPTH(1-84) between subjects of Japanese descent and matched non-Hispanic, Caucasian subjects, the differences of log-transformed PK parameters from the rhPTH(1-84) 100 μ g dose will be examined between the two ethnic groups using Welch's t-test with Satterthwaite's approximation to the degrees of freedom. The difference between the two means will be back transformed to provide an estimate for the geometric mean ratio and its 90% confidence interval (CI). The following PK parameters will be evaluated using this test: C_{max} and AUC_{last} based on original concentration, baseline-adjusted C_{max} , AUC_{last} , AUC_{0-inf} .

For C_{max} , AUC_{last} (original and baseline-adjusted) and AUC_{0-inf} (baseline-adjusted), Forest plots of geometric mean ratios (two-sided 90% CI) between Japanese cohort at 100 μ g vs Non-Japanese cohort at 100 μ g will be generated.

In addition, same Welch's t-test will be applied to compare the PK parameters between different doses and ethnic groups. The log-transformed dose-normalized AUC_{last} and C_{max} will be examined between the Japanese cohort at 50 μ g dose and the Non-Japanese cohort at 100 μ g as well as between the Japanese cohort at 25 μ g and the Non-Japanese cohort at 100 μ g. The geometric mean ratio estimates and their 90% CI will be provided from the model for each comparison.

Evaluation of Dose Proportionality (Exploratory)

Dose proportionality of baseline-adjusted PK parameters, will be examined for the Japanese subjects. Dose proportionality will be assessed for baseline-adjusted C_{max} , AUC_{last} , and

$AUC_{0-\infty}$, using the power model. The power model assumes a linear relationship between the natural log transformed parameter and the natural log transformed dose.

$$\ln(\text{Parameter}_{ijk}) = \alpha + \beta \times \ln(\text{Dose in } \mu\text{g}) + \pi_j + \gamma_i + \xi_{k(i)} + \varepsilon_{ijk} \quad (\text{Patterson and Jones, 2006})$$

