17. CHANGES TO ANALYSES SPECIFIED IN PROTOCOL

Section 9.8.1.1 (Statistical Analysis of Pharmacokinetic Parameters) of the protocol states that:

Dose proportionality of PK parameters will also be examined for the Japanese subjects. Dose proportionality will be assessed for C_{max} and AUC (AUC_{last}) using the power model. The power model assumes a linear relationship between the natural log transformed parameter and the natural log transformed dose.

$$\ln(\text{Parameter}) = \alpha + \beta \times \ln(\text{Dose}) + \text{Random error}$$

In order to compare the PKs of rhPTH(1-84) between subjects of Japanese descent and matched non-Hispanic, Caucasian subjects, the differences of log-transformed PK parameters from the rhPTH(1-84) 100 μ g dose will be examined between groups using an analysis of variance model.

However, to take account of the different sequences, the dose proportionality of PK parameters will be assessed by the power model with more factors:

$$\ln(\text{Parameter}_{ijk}) = \alpha + \beta \times \ln(\text{Dose in } \mu\text{g}) + \pi_j + \gamma_k + \xi_{k(i)} + \varepsilon_{ijk} \quad (\text{Patterson and Jones, 2006})$$

Where α is the intercept, β is the slope, π_j and γ_i identify the period j of sequence i , $\xi_{k(i)}$ is the random-intercept accounting for each subject within sequence as their own control, and ε_{ijk} denotes within-subject error. Dose proportionality will be assessed by estimating mean slope with the corresponding two-sided 90% confidence interval (CI) from the power model.

For the comparison of PKs between subjects of Japanese descent and matched non-Hispanic, Caucasian subjects, the differences of log-transformed PK parameters from the rhPTH(1-84) 100 μ g dose will be examined between the two ethnic groups using Welch's t-test with Satterthwaite's approximation to the degrees of freedom, rather than by ANOVA as stated in the protocol. The reason for this method of comparison is that the variance in the two ethnic groups is not expected to be the same.

Table 1 Schedule of Assessments from protocol states that randomization takes place on Day 4 for subjects of Japanese descent. It is changed to be on Day 1 in Table 1 in SAP.

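### The protocol's weight-adjusted PK comparison between ethnic groups is only descriptive in the SAP, and the SAP's weight-adjusted exposures adjust in the wrong direction if exposure under the flat dose falls with weight

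*Protocol*

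**What the plan says.** Protocol 3.2 gives its reason, "Due to the potential differences in body weight between enrolled subjects of Japanese descent and non-Hispanic, Caucasian subjects", and then its remedy: in addition to the unadjusted parameters, "we will also use body weight-adjusted PK parameters for comparison". Protocol 9.8.1 has AUClast, Cmax, CL/F and Vdz/F estimated with and without weight adjustment. Protocol 9.8.1.1 compares log-transformed parameters between groups at 100 µg by GMR and 90% CI, and in the same paragraph states: "Baseline-adjusted PK parameters will be the primary PK endpoints, and other PK parameters will be the secondary PK endpoints".

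SAP 12.3.3 derives the weight-adjusted parameters by dividing AUClast, AUC0-inf, Cmax, CL/F and Vdz/F by body weight. SAP 12.3.4.1 and Table 2.1.5 summarize them by ethnic group and dose. Weight-adjusted Cmax, AUClast and AUC0-inf also appear in side-by-side box plots at 100 µg.

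SAP 12.3.4.2 then sets the scope of the between-group Welch test: "The following PK parameters will be evaluated using this test". The list that follows is original Cmax and AUClast, and baseline-adjusted Cmax, AUClast and AUC0-inf. None is weight-adjusted and the test has no covariate. The forest plots and Tables 2.1.7 to 2.1.9 match that list. SAP 17 explains that groups will be compared by Welch's test "rather than by ANOVA as stated in the protocol", and records even a schedule footnote. It does not mention that the weight-adjusted comparison is descriptive only.

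**The concern.** The dose in the primary comparison is flat: "On Day 1, all study subjects will receive rhPTH(1-84) as a single 100" µg injection. If clearance rises with weight, lighter subjects have higher AUC and Cmax whatever their ethnicity.

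The matching does not remove this. "Non-Hispanic, Caucasian subjects will be matched to Japanese subjects based on sex, age" and BMI (±15%). Weight is BMI times height squared, so a pair of equal height may differ by 15% in weight, and a height difference adds to that.

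The Protocol synopsis says the results will guide dose selection for a later Phase 3 study in Japanese patients. Whether an exposure difference comes from weight or from ethnicity bears on that. The protocol foresaw the question, but the SAP does not answer it with the measure it uses for every other exposure comparison.

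**Working it through.** **Text check.** The plan states no sample-size calculation, margin or CV, so there is no planned figure to reproduce.

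| Element | Protocol | SAP |
|---|---|---|
| Weight-adjusted parameters derived | 9.8.1: yes | 12.3.3: yes |
| Summarized by group | 9.8.1.1: yes | 12.3.4.1, Table 2.1.5: yes |
| Used for comparison | 3.2: yes | Box plots and descriptive table only |
| Between-group GMR and 90% CI | 9.8.1.1: PK parameters, primary and secondary | 12.3.4.2: no weight-adjusted parameter |
| Recorded as a change | n/a | 17: no |

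**Direction of the SAP's adjustment.** Let r be the Japanese/Caucasian weight ratio, with CL/F proportional to weight^b and no ethnic effect. Both r and b are assumptions. The Japanese/Caucasian GMRs are:

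- unadjusted AUC: r^(-b)
- AUC/weight (the SAP's definition): r^(-(b+1))
- AUC × weight: r^(1-b)
- (CL/F)/weight: r^(b-1)

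At r = 0.85:

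| b | AUC | AUC/weight | AUC × weight | (CL/F)/weight |
|---|---|---|---|---|
| 1 | 1.18 | 1.38 | 1.00 | 1.00 |
| 0.75 | 1.13 | 1.33 | 0.96 | 1.04 |
| 0 | 1.00 | 1.18 | 0.85 | 1.18 |

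Dividing exposure by weight moves the ratio further from 1 in every row. The same algebra applies to Cmax with its own exponent. In 20,000 simulated trials (r = 0.85, b = 1, residual CV 30%, log-weight SD 0.12), the 90% CI excluded 1 in 34% for AUC, 65% for AUC/weight and 10% (nominal) for AUC × weight.

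**Size of the effect on the planned, unadjusted comparison.** The group sizes, 12 and 12, come from Protocol 3.1. A CV of 30% is assumed.

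- Log-scale SD: s = sqrt(ln(1 + 0.30²)) = 0.294.
- SE of the difference: 0.294 × sqrt(2/12) = 0.120.
- 90% CI factor: exp(1.717 × 0.120) = 1.23 (22 df). It is 1.15, 1.31 and 1.39 at CV 20%, 40% and 50%.

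Let R be the Caucasian/Japanese weight ratio, equal to (height ratio)² × BMI ratio. Assumed cases are 1.03² = 1.06, 1.05² = 1.10 and 1.05² × 1.05 = 1.16. The chance that the 90% CI contains 1 comes from a noncentral t with 22 df and shift b × ln(R)/0.120, the equal-variance stand-in for Welch:

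| R | Shift at b = 1 | CI contains 1, b = 1 | CI contains 1, b = 0.75 |
|---|---|---|---|
| 1.06 | 0.49 | 86% | 88% |
| 1.10 | 0.80 | 80% | 84% |
| 1.16 | 1.24 | 67% | 77% |

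With no weight effect (b = 0) the figure is 90%.

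**Cost of a weight covariate.** With within-group log-weight SD 0.12 (assumed), the variance of the adjusted difference is s² × (2/12 + (ln R)²/(22 × 0.12²)), with 21 df. At CV 30% the CI factor becomes 1.25 at R = 1.10, 1.28 at R = 1.16 and 1.35 at R = 1.27.

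**The case against.** The best defence is that the comparison is still there. Protocol 3.2 promises comparison, not a test or an interval, and the descriptive sentence of Protocol 9.8.1.1 is the only place there that names weight-adjusted parameters. The SAP tabulates them by group with geometric means, geometric CVs and 95% CIs, box-plots the exposures at 100 µg and lists them all. This stands in part. A reader might infer that the SAP abandoned the weight-adjusted comparison. It did not; it reduced it to descriptive form. What is missing is a between-group ratio with its interval, and a line in SAP 17 saying so.

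A reader might also infer that the study cannot separate weight from ethnicity. That goes too far. Table 2.1.5 gives n, geometric mean and geometric CV of (CL/F)/weight in each group, from which a Welch ratio could be worked out by hand. The defence does not extend to AUC/weight and Cmax/weight, which move the wrong way.

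Nor do the documents show that a weight difference *will* be read as ethnic. SAP 7 tabulates weight by group, SAP 2.6 calls the analyses exploratory, and no decision depends on the CI containing 1. A more alarming figure, 39% of intervals containing 1, arises at R = 1.05² × 1.15 = 1.27, but it needs nearly every pair at the same edge of a symmetric BMI window, plus a 5% height difference and exponent 1.

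Finally, unadjusted exposure is a legitimate main contrast. The marketed doses are flat, and higher exposure at the same dose matters even if weight causes it. That stands, and is why the adjusted result should be secondary.

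**Conclusion.** The point holds in this form. Protocol 3.2 commits to weight-adjusted parameters for the group comparison, the SAP provides them only descriptively, and SAP 17 is silent. This rests on the text alone.

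The second part is technical. Under a flat dose, AUC/weight and Cmax/weight enlarge a weight imbalance when exposure falls with weight, so the descriptive exposure output does not fill the gap. Only (CL/F)/weight and (Vdz/F)/weight correct for it.

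The consequence is a risk, not a certainty. At equal BMI and an assumed 3 to 5% height difference (R of 1.06 to 1.10) the unadjusted interval contains 1 in about 80 to 86% of trials with no ethnic effect, and at R = 1.16 in 67%. These figures rest on assumed values for the weight ratio, exponent 1 and CV 30%. The change should be made, but it does not undermine the unadjusted primary analysis.

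**What to change.** 1. In SAP 12.3.4.2 add a secondary analysis at 100 µg: log baseline-adjusted Cmax, AUClast and AUC0-inf on ethnic group and log Day -1 weight, with group-specific residual variances so that the SAP's reason for choosing Welch is respected. Report the GMR and 90% CI beside the unadjusted Welch result in Table 2.1.7 and the forest plot.
2. As an addition or alternative, give a Welch GMR and 90% CI for (CL/F)/weight. It fixes the exponent at 1, so it over-corrects if exposure depends less on weight (see the b = 0 row). It also does not cover Cmax, and it is lost for subjects whose CL/F is not calculated under SAP 12.3.3.
3. Do not run the Welch test on AUC/weight or Cmax/weight. Replace those definitions with exposure normalized to dose per kg (AUC × weight/dose, Cmax × weight/dose), or state their limitation.
4. Record the change in SAP 17.

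The cost is a few lines of SAP text and one block in an existing table; weight is already measured at screening and Day -1. The statistical price is one degree of freedom and a wider interval: a CI factor of about 1.25 to 1.28 instead of 1.23 at R of 1.10 to 1.16, and about 1.35 at 1.27, under the assumptions above. Adjustment is least precise where the imbalance is largest, so the unadjusted result should stay as the main analysis.

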3.3 Duration and Study Completion Definition

The subject's maximum duration of participation is expected to be approximately 62 days for the non-Hispanic, Caucasian volunteers and 68 days for the subjects of Japanese descent. The study will be completed in approximately 9 weeks.

The Study Completion Date is defined as the date the final subject, across all sites, completes their final protocol-defined assessment. Please note that this includes the follow-up visit or contact, whichever is later. The Study Completion Date is used to ascertain timing for study results posting and reporting.

